### Contraception

Females of reproductive potential must commit either to abstain continuously from heterosexual sexual intercourse or to use 2 methods of effective contraception simultaneously (1 highly effective form of contraception—tubal ligation, intrauterine device [IUD], hormonal [birth control pills, injections, hormonal patches, vaginal rings or implants] or partner's vasectomy and 1 additional effective contraceptive method—male latex or synthetic condom, diaphragm, or cervical cap). Contraception must begin 4 weeks prior to initiating treatment and continue during therapy, dose interruptions, and for 30 days after discontinuation of therapy. Reliable contraception is indicated even where there has been a history of infertility, unless this is due to hysterectomy. Females of reproductive potential should be referred to a qualified provider of contraceptive methods, if needed. Additional details are provided in Pomalidomide Risks of Fetal Exposure, Pregnancy Testing Guidelines and Acceptable Birth Control Methods ([Appendix H](#)), Pomalidomide Education and Counseling Guidance Document ([Appendix I](#)), and Pomalidomide Information Sheet for Subjects Enrolled in Clinical Research Studies ([Appendix J](#)).

Females of reproductive potential must have 2 negative pregnancy tests before initiating study treatment. The first test should be performed within 10 to 14 days of study treatment and the second test should be performed within 24 hours before study treatment. Once treatment has started and during dose interruptions, pregnancy testing for female subjects of reproductive potential should occur weekly during the first 4 weeks of treatment. Pregnancy testing should be repeated every 4 weeks thereafter for female subjects with regular menstrual cycles. For female subjects with irregular menstrual cycles,  $\pm$  7 days of a 28-day cycle, pregnancy testing should be performed every 2 weeks. Pregnancy testing and counseling should be performed if a subject misses her period or if there is any abnormality in her menstrual bleeding. Study treatment must be discontinued during this evaluation.

---

Postmenopausal females (> 45 years old and without menses for > 2 years) and surgically sterilized females are exempt.

Male subjects must use an effective barrier method of contraception during the study and for 90 days following the last dose if sexually active with a female of childbearing potential.

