8 Pomalidomide will be administered on Days 1 to 21 of each 4 week cycle and may be taken with or without food. Once there is a first dose level of oprozomib determined to be safe in combination with pomalidomide and dexamethasone (as determined by the first cohort in Part 2), the Part 1 subjects will be allowed to add pomalidomide to their treatment at that particular dose level.

9 PK samples should be collected at the exact nominal time point as noted. The permitted time windows for PK postdose collection C1D8 and C1D22 are:  $\pm$  5 minutes for the 0.5 and 1 hour time points,  $\pm$  10 minutes for the 2 hour time point and  $\pm$  20 minutes thereafter. The C1D8 8 hour post dose, the C1D9 pre-dose and C1D23 pre-dose PK collections will occur only for the subjects taking the GR formulation.

10 Safety lab tests will include chemistry, hematology, coagulation and urinalysis. If acceptable screening laboratory assessments are within 48 hours of study day 1, the pre-dose laboratory assessments do not need to be obtained. If a subject has a grade 3 hypophosphatemia, a repeat phosphate level test within 24 hours is required to rule out DLT.

11 Females of childbearing potential only: Serum pregnancy test performed at screening; urine or serum pregnancy test at all other timepoints. See Section 9.6

12 All subjects will be tested for HBsAG, antiHBcAb, and HCVAb. If HBsAg is negative and HBcAb is positive, test HBV DNA by PCR. If HCVAb is positive, test HCV RNA by PCR.

13 Immunofixation is done at screening and is required at next assessment only if SPEP or UPEP results are zero or undetectable.

14 Quantitative Immunoglobulin (Total IgG, IgA and IgM) is obtained at screening and will be repeated if clinically indicated (i.e, frequent infection despite multiple myeloma disease control).

15 A bone marrow sample will be collected from all subjects during screening for fluorescent in situ hybridization (FISH), to quantify percent myeloma involvement. Part of the bone marrow sample will also be used for the [REDACTED]. An additional bone marrow sample will only be required to confirm a complete response (CR). Samples can be collected during screening up to pre-dose of cycle 1 day 1. [REDACTED]

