### Criteria for Females of Childbearing Potential (FCBP)

This protocol defines a female of childbearing potential as a sexually mature woman who: 1) has not undergone a hysterectomy or bilateral oophorectomy or 2) has not been naturally postmenopausal (amenorrhea following cancer therapy does not rule out childbearing potential) for at least 24 consecutive months (ie, has had menses at any time in the preceding 24 consecutive months).

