**During study participation and for 28 days following study drug discontinuation**

**Female Subjects**

- Females of childbearing potential with regular or no menstrual cycles must agree to have pregnancy tests weekly for the first 28 days of study participation and then every 28 days while on study, at study discontinuation, and at Day 28 following study drug discontinuation. If menstrual cycles are irregular, the pregnancy testing must occur weekly for the first 28 days and then every 14 days while on study, at study discontinuation, and at Days 14 and 28 following study drug discontinuation.
- At each visit, the investigator must confirm with the FCBP that she is continuing to use 2 reliable methods of birth control.
- Counseling about pregnancy precautions and the potential risks of fetal exposure must be conducted at a minimum of every 28 days.
- If pregnancy or a positive pregnancy test does occur in a study subject, pomalidomide must be immediately discontinued.
- Pregnancy testing and counseling must be performed if a subject misses her period or if her pregnancy test or her menstrual bleeding is abnormal. Study drug treatment must be discontinued during this evaluation.
- Females must agree to abstain from breastfeeding during study participation and for at least 28 days after study drug discontinuation.

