**FCBP**

1. **I verified that the required pregnancy tests performed are negative.**
2. **I counseled FCBP regarding the following:**
  - Potential fetal harm: If pomalidomide is taken during pregnancy, it may cause birth defects or death to any unborn baby. Females are advised to avoid pregnancy while taking pomalidomide. The teratogenic potential of pomalidomide in humans cannot be ruled out. Females of childbearing potential must agree not to become pregnant while taking pomalidomide.
  - Using TWO reliable methods of birth control at the same time or complete abstinence from heterosexual intercourse [at least 28 days prior, while taking pomalidomide, during dose interruption, and 28 days after discontinuation of pomalidomide].
  - Continuation of TWO reliable methods of birth control or complete abstinence if therapy is interrupted.
  - That even if she has amenorrhea she must comply with advice on contraception.
  - Use of one highly effective method and one additional method of birth control AT THE SAME TIME. The following are examples of highly effective and additional effective methods of contraception:

- Highly effective methods:
  - Intrauterine device (IUD)
  - Hormonal (birth control pills, injections, implants)
  - Tubal ligation
  - Partner's vasectomy
- Additional effective methods:
  - Male condom
  - Diaphragm
  - Cervical cap
- Pregnancy tests before and during treatment, even if the patient agrees not to have reproductive heterosexual intercourse. Two pregnancy tests will be performed prior to receiving study drug, one within 10–14 days and the second within 24 hours of the start of pomalidomide.
- Frequency of pregnancy tests to be done:
  - Every week during the first 28 days of this study and a pregnancy test every 28 days during the patient's participation in this study if menstrual cycles are regular or every 14 days if cycles are irregular.
  - If the patient missed a period or has unusual menstrual bleeding.
  - When the patient is discontinued from the study and at Day 28 after study drug discontinuation if menstrual cycles are regular. If menstrual cycles are irregular, pregnancy tests will be done at discontinuation from the study and at Days 14 and 28 after study drug discontinuation.
- Stop taking pomalidomide immediately in the event of becoming pregnant and to call their study doctor as soon as possible.
- NEVER share pomalidomide with anyone else.

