**3. Provide Pomalidomide Information Sheet to the patient.**

**Female not of childbearing potential (natural menopause for at least 24 consecutive months, a hysterectomy, or bilateral oophorectomy):**

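### Weekly pregnancy testing is not restarted when a Part 1 woman adds pomalidomide, and the Section 9.6 exemption omits the appendices' rule on amenorrhea after cancer therapy (minor safety fix)

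*Protocol*

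**What the plan says.** **Timing of tests.** Protocol Section 9.6 (Contraception) says that testing "should occur weekly during the first 4 weeks of treatment", then every 4 weeks, or every 2 weeks if cycles are irregular. Section 9.2 defines study treatment as any combination of the three drugs, so oprozomib with dexamethasone starts that clock. Appendix H counts from study participation: "Females of childbearing potential with regular or no menstrual cycles must agree to have pregnancy tests weekly for the first 28 days". Appendix I also counts from the start of the study.

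Section 10.2.19 excludes Part 1 subjects from pomalidomide in cycle 1. Section 9.3.1.1 lets them add it only once the first Part 2 cohort has shown a dose level to be safe.

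Appendix H (Before starting study drug) requires two negative tests, one 10 to 14 days and one within 24 hours before pomalidomide. Section 9.6 asks for the same pair but ties it to study treatment.

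**Who is exempt.** Section 9.6 states: "Postmenopausal females (> 45 years old and without menses for > 2 years) and surgically sterilized females are exempt". Appendix H, in defining a female of childbearing potential (FCBP), adds that "amenorrhea following cancer therapy does not rule out childbearing potential", and the Appendix I form repeats this. Appendix I counsels an FCBP "That even if she has amenorrhea she must comply with advice on contraception". Its entry for women not of childbearing potential lists "natural menopause for at least 24 consecutive months, a hysterectomy, or bilateral oophorectomy". Footnote 11 of Table 6 reads "Females of childbearing potential only: Serum pregnancy test performed at screening; urine or serum pregnancy test at all other timepoints. See Section 9.6", and Section 9.6 in turn sends the reader to Appendices H, I and J for further detail.

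**The concern.** Pomalidomide is the reason for intensive pregnancy testing, and Appendix H describes it as teratogenic in rabbits and an analogue of a known human teratogen. Weekly testing is useful when it covers the first weeks of exposure. For a Part 2 woman it does, because she takes pomalidomide from day 1. For a Part 1 woman the weekly series falls in weeks when she is not on pomalidomide, and her testing drops to monthly or fortnightly at about the point where exposure begins, or earlier.

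The exemption raises a second, smaller issue. Eligible women have had at least two prior lines of therapy, so amenorrhea caused by treatment is foreseeable. A site that read only Section 9.6 could treat such a woman over 45 as exempt, although the appendices keep her as FCBP. The trigger for testing after a missed period cannot operate in a woman without menses, although the trigger for abnormal bleeding still can.

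**Working it through.** The plan states no figure for this point. The check is a count of days and tests, followed by a comparison of the two exemption rules.

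**1. Weekly window against first pomalidomide dose**

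- Weekly window: study days 1 to 28 (Section 9.6, Appendices H and I).
- Earliest Part 1 pomalidomide dose: cycle 2 day 1, nominal day 29 (Section 10.2.19). The visit window is ±2 days, so days 27 to 31.
- Overlap of the weekly window with pomalidomide: 0 days nominally; at most 2 days (27 and 28) at the window edge.
- IR cohort: the Part 2 starting dose depends on Part 1 (Section 6.1), and each part has a 28-day DLT window (Section 9.2.1.4). The earliest start is therefore about day 28 + 28 + 1 = 57.

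**2. Scheduled tests in the first 28 days on pomalidomide, from the readable text**

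| Woman | Interval | Tests |
|---|---|---|
| Part 2 FCBP | 7 days | 28/7 = 4 |
| Part 1 FCBP, regular or no cycles | 28 days | 28/28 = 1 |
| Part 1 FCBP, irregular cycles | 14 days | 28/14 = 2 |

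The shortfall is 4 − 1 = 3 or 4 − 2 = 2 tests.

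**3. Cross-check against Table 7**

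Table 7 budgets 16 serum pregnancy tests, and its total assumes 10 cycles plus screening and end of study. One breakdown that fits is 2 before treatment + 4 weekly in cycle 1 + 9 for cycles 2 to 10 + 1 at end of study = 16 (16 × 3 mL = 48 mL, as tabulated). That leaves no second weekly series. It agrees with the text but does not prove the schedule.

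**4. Upper limit on numbers**

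Table 2 shows 5 IR + 8 GR = 13 subjects in the oprozomib-dexamethasone group, of both sexes. The absolute ceiling is 13 × 3 = 39 extra tests. This is not an estimate: it counts men and women who are not FCBP.

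**5. The exemption rules side by side**

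| Example | Section 9.6 | Appendices H and I |
|---|---|---|
| Age 48, 3 years of amenorrhea after chemotherapy | Exempt on the words in parentheses | FCBP |
| Age 44, natural menopause for 30 months | Not exempt | Not FCBP (Appendix I entry) |

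Only the first row could remove testing that the appendices require. In the second row Section 9.6 is the stricter rule.

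**The case against.** The strongest reply is that the safeguards already cover most of the risk, and much of it stands.

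- **Tests before pomalidomide.** A reader might infer that a Part 1 woman could start pomalidomide untested. The documents do not support that: Appendix H ties two negative tests to the start of pomalidomide. Section 9.6 uses a different starting point, but a Part 1 subject can satisfy both. The gap is confined to the weeks after the start.
- **The dispensing form.** A reader might also infer that the two exemption rules leave women with therapy-induced amenorrhea untested. The Appendix I form is completed before each dispensing, makes the site classify the woman under the FCBP definition, and bars dispensing to an FCBP with no pregnancy test. Appendix H limits each dispensing to one cycle. The form sets no weekly frequency, however, so it does not answer the timing point.
- **Section 9.6 is not lax in spirit.** It wants contraception even with a history of infertility unless this is due to hysterectomy. That sentence concerns contraception and not testing, but it weighs against a loose reading of the exemption.
- **Tubal ligation and the 'or'.** It is tempting to read surgical sterilization as exempting women with tubal ligation, but Section 9.6 lists tubal ligation as a contraceptive method. Appendix H joins its criteria as "1) has not undergone a hysterectomy or bilateral oophorectomy or 2) has not been naturally postmenopausal"; taken literally, this would make nearly every woman FCBP, which errs towards more testing. The Appendix I list shows the intent. Both are clerical.
- **Unseen material.** The Table 6 grid and Appendix J are not visible. Day 15 visits exist in cycles 2 to 4, and whether they include a pregnancy test cannot be seen.
- **Stage of the trial.** Section 5.5.5 reports results from a study report with an August 2020 snapshot, and Section 6.5.2 places the primary analysis after target enrollment is complete. Few or no Part 1 women may still be about to add pomalidomide.

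**Conclusion.** The timing point holds. On the readable text, a Part 1 woman of childbearing potential who adds pomalidomide has about 1 or 2 scheduled tests in her first 28 pomalidomide days instead of about 4, because her weekly series has ended or is ending. This assumes that the unseen Table 6 grid adds no tests beyond the text.

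The exemption point holds only in part. Section 9.6 fails to carry the appendices' rule on amenorrhea after cancer therapy. The group exposed is women over 45, without menses for more than 2 years, whose amenorrhea is treatment-related, and the Appendix I form largely catches them.

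This is a minor safety fix. Two contraceptive methods or abstinence, counselling, the pre-pomalidomide tests and the dispensing check all remain in force. The documents give no sex or age distribution, so the number of women affected cannot be estimated; it cannot exceed the 13 Part 1 subjects for timing and may now be nil.

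**What to change.** 1. In Section 9.6 and Appendices H and I, require 28 days of weekly testing from the first pomalidomide dose as well as from study day 1.
2. In Section 9.6, repeat the two pre-pomalidomide tests from Appendix H.
3. Use one definition of a woman not of childbearing potential, and point Section 9.6 and Table 6 footnote 11 to it: natural menopause for at least 24 months, hysterectomy or bilateral oophorectomy, with amenorrhea after cancer therapy not counting. Keep the over-45 floor for natural menopause and add it to the appendices, so that no woman loses testing she now has.
4. As clerical clarifications, say that tubal ligation is a contraceptive method and not an exemption, and align the 'or' in the Appendix H and I definitions with the Appendix I list.

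The cost is amendment wording in those places and 2 to 3 urine or serum tests for each Part 1 woman who still adds pomalidomide. Keeping the age floor also means that naturally postmenopausal women aged 45 or under, whom the appendices alone would not test, continue to be tested.

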#### **9.7            Tobacco Restrictions**

Cigarette smoking may reduce pomalidomide exposure due to CYP1A2 induction. Subjects should be advised that smoking may reduce the efficacy of pomalidomide.

#### **9.8            Product Complaints**

A product complaint is any written, electronic or oral communication that alleges deficiencies related to the identity, quality, durability, reliability, safety, effectiveness, or performance of a drug(s) or device(s) after it is released for distribution to market or clinic by either Amgen or by distributors and partners for whom Amgen manufactures the material. This includes any drug(s) or device(s) provisioned and/or repackaged /modified by Amgen. Drug(s) or device(s) includes investigational product.

Any product complaint(s) associated with an investigational product(s) or non-investigational product(s) supplied by Amgen are to be reported according to the instructions provided in the IPIM.

#### **9.9            Excluded Treatments, Medical Device Use, and/or Procedures During Study Period**

Drug interactions may occur with concomitant use of certain medications with pomalidomide. Refer to the Pomalidomide Prescribing Information for current guidance on dosing restriction or adjustment recommendations.

Glucocorticoid therapy that exceeds a cumulative dose of 160 mg of dexamethasone is not permitted within 21 days prior to enrollment. During the study, glucocorticoid therapy (in addition to dexamethasone) is only permitted upon discussion with the Amgen study medical monitor to treat a concurrent medical condition (eg, asthma, inflammatory bowel disease, emesis, etc.).

---

Other antimyeloma or investigational agents are not permitted prior to the subject developing confirmed progressive disease.

Treatment with drugs associated with increased risk of GI hemorrhage should be based on an assessment of underlying risks.

Plasmapheresis is not permitted at any time during the screening period or while the subject is receiving study treatment. If a subject has started screening procedures and requires plasmapheresis, or is anticipated to require plasmapheresis during or after the screening period, this patient will be considered ineligible and should not be enrolled. Subjects requiring plasmapheresis while on study treatment should have every attempt made to document progressive disease by IMWG criteria first, and then will discontinue study treatment. Study procedures required at EOS should be done.

**10. STUDY PROCEDURES**

**10.1 Schedule of Assessments**

**Table 6. Schedule of Assessments**

Footnotes defined on next page

1 Visit windows: A +/-1 day window is allowed for C1D8, C1D15, C1D22, C2D15, C3D15 and C4D15, however study treatment dosing must occur on two sequential days. Starting with C2, there is a +/-2 day window for D1 of every cycle.

2 Clinical evaluation will include: physical exam with a neurologic assessment, ECOG status and weight. At screening only: medical and surgical history and height.

3 Vital signs (blood pressure, respiratory rate, heart rate, temperature) will be collected after the subject has rested for at least 5 minutes.

4 ECG will be performed after subject has rested for approximately 5 minutes in the supine position; ECG performed in triplicate (approximately 30 seconds apart and run consecutively, interval between tracings should not be greater than 60 seconds) at all timepoints, reporting PR, QRS, QT, QTc, RR interval. Subjects receiving 270 mg or higher dose of oprozomib IR formulation in combination with pomalidomide and dexamethasone, must have ECG done 1 and 2 hours after oprozomib doses on Cycle 1 Day 1, Cycle 1 Day 8 and Cycle 2 Day 1. After cycle 2, ECGs are only required if clinically indicated, unless specified on the SOA. If interval prolongation > 480 msec occurs (and is a 30 msec increase above baseline), subject's serum potassium, magnesium, calcium and phosphorus should be measured immediately and replaced if needed.

5 Required at screening only.

6 Refer to [Appendix G](#) for the evaluation tool. The site will enter the score to each question on the eCRF and the total score will be derived in electronic database.

7 Each complete cycle will be 4 weeks (28 days duration) comprising 8 dose administrations of oprozomib and dexamethasone: days 1, 2, 8, 9, 15, 16, 22 and 23. It is recommended that oprozomib IR be taken after a low fat meal. The GR formulation must be taken immediately after a main meal that contains the highest calorie and fat content. Dexamethasone may be taken at the same time as oprozomib. On PK collection days, the time of meal intake will be recorded on the eCRF. Subjects must be advised to take meals prior to dosing.

8 Pomalidomide will be administered on Days 1 to 21 of each 4 week cycle and may be taken with or without food. Once there is a first dose level of oprozomib determined to be safe in combination with pomalidomide and dexamethasone (as determined by the first cohort in Part 2), the Part 1 subjects will be allowed to add pomalidomide to their treatment at that particular dose level.

9 PK samples should be collected at the exact nominal time point as noted. The permitted time windows for PK postdose collection C1D8 and C1D22 are:  $\pm$  5 minutes for the 0.5 and 1 hour time points,  $\pm$  10 minutes for the 2 hour time point and  $\pm$  20 minutes thereafter. The C1D8 8 hour post dose, the C1D9 pre-dose and C1D23 pre-dose PK collections will occur only for the subjects taking the GR formulation.

10 Safety lab tests will include chemistry, hematology, coagulation and urinalysis. If acceptable screening laboratory assessments are within 48 hours of study day 1, the pre-dose laboratory assessments do not need to be obtained. If a subject has a grade 3 hypophosphatemia, a repeat phosphate level test within 24 hours is required to rule out DLT.

11 Females of childbearing potential only: Serum pregnancy test performed at screening; urine or serum pregnancy test at all other timepoints. See Section 9.6

12 All subjects will be tested for HBsAG, antiHBcAb, and HCVAb. If HBsAg is negative and HBcAb is positive, test HBV DNA by PCR. If HCVAb is positive, test HCV RNA by PCR.

13 Immunofixation is done at screening and is required at next assessment only if SPEP or UPEP results are zero or undetectable.

14 Quantitative Immunoglobulin (Total IgG, IgA and IgM) is obtained at screening and will be repeated if clinically indicated (i.e, frequent infection despite multiple myeloma disease control).

15 A bone marrow sample will be collected from all subjects during screening for fluorescent in situ hybridization (FISH), to quantify percent myeloma involvement. Part of the bone marrow sample will also be used for the [REDACTED]. An additional bone marrow sample will only be required to confirm a complete response (CR). Samples can be collected during screening up to pre-dose of cycle 1 day 1. [REDACTED]

17 For subjects with a history of extramedullary disease, plasmacytoma evaluation is to be repeated during treatment only to confirm a response of PR or better, to confirm PD, or if clinically indicated. The same technique used during screening must be employed for each measurement (may include ultrasound, CT scan, MRI, PET or other standard of care method). Assessment by physical examination at screening is acceptable.

18 Bone lesion assessment to be repeated Q8W if clinically indicated (i.e, new symptoms of bone pain arise). Consider obtaining an MRI for subjects with bone pain if the skeletal survey is normal.

---

19 End of Study: visit should be performed approximately 30 (+7) days after the last dose of study drug.

